**5.3.1.6. Ibrutinib/Placebo Hold after Withdrawal of All Immunosuppressants**

At the physician's discretion, ibrutinib/placebo may be held if ALL of the following conditions are met:

- All systemic immunosuppressants used for the treatment of cGVHD have been discontinued. (The continued use of very low doses of corticosteroids used only for physiologic adrenal replacement is allowed)
- cGVHD response has been maintained for 12 weeks after complete withdrawal of all immunosuppressants (not including ibrutinib/placebo)
- The subject has received a minimum of 48 weeks of ibrutinib/placebo

If cGVHD returns/worsens after ibrutinib/placebo has been held for the above criteria, ibrutinib/placebo may be re-started after consulting with the medical monitor.

### **5.3.2. Prednisone**

#### **5.3.2.1. Formulation/Packaging/Storage**

Prednisone tablets for oral administration are available in multiple strengths. Commercially available prednisone will be supplied by the Sponsor where applicable. The commercial material will be relabeled for clinical trial use.

For situations where a subject who must receive an IV or alternate formulation of corticosteroid (eg, hospitalization for AE), the dose should be equivalent to the subject's prednisone dose using the prednisone equivalency table ([Appendix K](#)) unless the subjects clinical condition warrants a different dose (eg, stress doses of steroids for sepsis). All doses of corticosteroids must be entered into the eCRF.

Refer to the Pharmacy Manual for additional guidance on prednisone storage, preparation and handling.

#### **5.3.2.2. Dose and Administration**

Prednisone will be given orally at 1.0 mg/kg/d with rounding to multiples of 5 mg (eg, 15, 20, 25, etc.).

If a prednisone dose of 1.0 mg/kg/d is contraindicated (eg, poorly controlled diabetes, major mood disturbances) then the starting dose of prednisone may be reduced to 0.5-1.0 mg/kg/d. Subjects unable to receive a starting dose of prednisone of at least 0.5 mg/kg/d are ineligible for the study.

If, during Screening, the clinical condition of the subject requires immediate initiation of treatment with prednisone, prednisone may be started prior to randomization. If the subject begins prednisone during Screening and prior to randomization the eligible subject must be randomized within 7 days of starting prednisone.

If a subject has started corticosteroids within the 72 hours prior to consent, then the subject is eligible and can continue corticosteroids after signing consent but must be randomized within 7 days of signing consent.

##### **5.3.2.2.1. Prednisone Taper**

Prednisone taper should be attempted by the schedule outlined in [Table 4](#):

**Table 4. Prednisone Taper Schedule**

Study Week #	Dose (mg/kg, body weight)
0	1.0 qd
2	0.75 qd
4	0.65 qd
6	0.50 qd
8	0.70 qod*
10	0.55 qod
12	0.45 qod
14	0.35 qod
16	0.25 qod
18	0.20 qod
20	0.15 qod
22	0.10 qod
24	0.0

\*qod=every other day. #Timing of steroid taper is defined by when the first dose of prednisone is given.

The prednisone taper should commence by week 2, but it is understood that considerable variation in prednisone taper will occur depending on the subjects' response and other intercurrent illnesses. More rapid tapering of prednisone doses is allowed if clinically appropriate. Rounding of corticosteroid doses is acceptable. Decisions about the use of qod or alternative dosing schedules (eg, Mon/Wed/Fri) may follow institutional practice. Prednisone taper should be completed prior to tapering of other immunosuppressants unless the clinical condition of the subject dictates tapering/discontinuing other medications sooner (eg, toxicity associated with the use of the medication).

#### 5.3.2.2.2. Flares in cGVHD

Exacerbation of cGVHD symptoms may occur during prednisone taper or with intercurrent illnesses. Temporary re-escalation of prednisone dose is allowed at the physician's discretion. Tapering of increased prednisone dose for a flare should begin within 4 weeks.

#### 5.3.2.3. Overdose

The effects of accidental ingestion of large quantities of prednisone over a very short period of time have not been reported, but prolonged use of the drug can produce mental symptoms, moon face, abnormal fat deposits, fluid retention, excessive appetite, weight gain, hypertrichosis, acne, striae, ecchymosis, increased sweating, pigmentation, dry scaly skin, thinning scalp hair, increased blood pressure, tachycardia, thrombophlebitis, decreased resistance to infection, negative nitrogen balance with delayed bone and wound healing, headache, weakness, menstrual disorders, accentuated menopausal symptoms, neuropathy, fractures, osteoporosis, peptic ulcer,

decreased glucose tolerance, hypokalemia, and adrenal insufficiency. Hepatomegaly and abdominal distention have been observed in children.

Treatment of acute overdosage is by immediate gastric lavage or emesis followed by supportive and symptomatic therapy. For chronic overdosage in the face of severe disease requiring continuous steroid therapy the dosage of prednisone may be reduced only temporarily, or alternate day treatment may be introduced.

#### **5.3.2.4. Dose Modification for Adverse Reactions**

Prednisone will be tapered by study design according to clinical response in cGVHD (Table 4). Prednisone suppresses the hypothalamic-pituitary-adrenal (HPA) axis and, therefore, doses must be tapered slowly after long-term use. The occurrence of unmanageable adverse reactions from prednisone (eg, poorly controlled hypertension) may require a more rapid reduction in prednisone dosing, but may not necessitate a change in dose of study drug (ibrutinib/placebo). Dose modifications will be at the discretion of the physician and should reflect a balance of appropriately treating cGVHD and minimizing adverse effects.

#### **5.4. Criteria for Permanent Discontinuation of Ibrutinib/Placebo**

Investigators are encouraged to keep a subject who is experiencing clinical benefit in the study unless significant toxicity puts the subject at risk or routine noncompliance puts the study outcomes at risk. For a complete list of criteria for permanent discontinuation of ibrutinib/placebo, refer to Section 9.2.

An End-of-Treatment visit (Section 8.2.3) is required for all subjects except for those subjects who have withdrawn full consent.

### **6. CONCOMITANT MEDICATIONS/PROCEDURES**

Concomitant therapies must be recorded from 30 days prior to signing of the ICF through 30 days after the last dose of study treatment (ibrutinib/placebo or corticosteroids), start of another therapy for cGVHD, or start of a new therapy for progression for the underlying malignancy.

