##### **7.1.1.4. Prior and Concomitant Medications**

All medications from 30 days prior to signing of ICF through 30 days after the last dose of ibrutinib/placebo or prednisone, start of another therapy for cGVHD, or start of a new therapy for progression of underlying malignancy will be documented.

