#### **8.3.1. Response Follow-up**

Subjects who discontinue ibrutinib/placebo for reasons other than progressive cGVHD or progression of underlying malignancy will be followed at pre-specified response assessment time points (Weeks 5, 13, 25 and every 12 weeks thereafter) by clinic visit until progressive disease or progression of underlying malignancy. During this period, the following procedures will be performed:

- Physical examination
- Vital signs
- Performance status (KPS/Lansky) ([Appendix C](#))
- Hematology
- Serum chemistry
- cGVHD activity assessment per NIH ([Appendix H](#) and [Appendix J](#))
- cGVHD response assessment ([Appendix I](#))
- Lee cGVHD Symptom Scale ([Appendix F](#))/SF-36 Questionnaire ([Appendix G](#))
- FEV1 every 12 weeks if prior FEV1 abnormal, every 24 weeks if prior FEV1 normal
- Review corticosteroid requirements and any new cGVHD treatment if applicable

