Time to withdrawal of all corticosteroids for treatment of cGVHD	
Time from randomization until the date of complete withdrawal (to 0mg) of corticosteroids used to treat GVHD and sustained for 30 days. Subjects will be considered having a competing risk at the time of death, relapse of the underlying disease, progression of cGVHD, or start of subsequent cGVHD therapy. Subjects with no competing event will be censored at last available study visit.
	
The two Cumulative Incidence Functions (CIFs) of corticosteroid withdrawal will be compared using Gray's Chi square test.
 
Graphs of the CIFs and landmark estimates (95%) at 6 months and 12 months
	ITT

Endpoint	Definition	Analysis Method	Population
		obtained from the CIFs will be provided.	
Time to withdrawal of all ISTs, including corticosteroids for treatment of cGVHD (with the exception of ibrutinib/placebo)	Time from randomization until the date of complete withdrawal (to 0mg) of all corticosteroids used to treat GVHD AND discontinuation of all ISTs sustained for 30 days. Subjects will be considered having a competing risk at the time of death, relapse of the underlying disease, progressive disease (PD) of cGVHD, or start of subsequent cGVHD therapy. Subjects with no competing event will be censored at last available study visit	The two CIFs of withdrawal of all immunosuppressants will be compared using Gray's Chi square test. Graphs of the CIFs and landmark estimates (95%) at 6 months and 12 months obtained from the CIFs will be provided	ITT
Response rate at 24 weeks	
Proportion of responders [complete response (CR) or partial response (PR)] as assessed by investigators at 24 weeks using the NIH Consensus Panel Chronic GVHD Activity Assessment.
 
A subject will NOT be considered as a responder at 24 weeks if he/she meets any of following criteria:
 
 Starts a second line systemic therapy for cGVHD at or prior to the response assessment at 24 weeks Has evidence of progression of the underlying malignancy that was the indication for transplant at or prior to response assessment at 24 weeks 
Subjects withdrawing from the study or from response assessment prior to 24 weeks.
	Comparison of the proportions between the two arms will be performed using Chi-square test	ITT

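### Stop dates of non-steroid immunosuppressants need not be recorded once study treatment has ended, yet the gated endpoint that needs them keeps subjects at risk to the last visit

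*Protocol*

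**What the plan says.** **Recording window.** Protocol Section 6 has concomitant therapies recorded "through 30 days after the last dose of study treatment (ibrutinib/placebo or corticosteroids), start of another therapy for cGVHD", or new therapy for malignancy progression. Section 7.1.1.4 gives the same window: "All medications from 30 days prior to signing of ICF through 30 days after the last dose of ibrutinib/placebo or prednisone". Neither section says whether 'or' means the earlier or the later of the two drugs. Section 10.5 settles this as the later one, but only for the treatment-emergent adverse event period.

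**Follow-up visits.** The Treatment, Progressive Disease and End-of-Treatment visit lists (8.2.1 to 8.2.3) all include a review of concomitant medications. The Response Follow-up list (8.3.1) has instead: "Review corticosteroid requirements and any new cGVHD treatment if applicable". An immunosuppressant already in use at entry, which Section 6.1.2 permits, is neither of these.

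**Taper order.** The text under Table 4 says: "Prednisone taper should be completed prior to tapering of other immunosuppressants", with an exception where the subject's condition dictates otherwise. Section 6.1.2 allows the other agents to be tapered from the start of study treatment.

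**Endpoint.** SAP Section 1.6 places time to withdrawal of all ISTs third in the serial order. Table 2 requires steroids at zero and all ISTs stopped, sustained for 30 days. Competing events are death, relapse, cGVHD progression and subsequent cGVHD therapy. For everyone else: "Subjects with no competing event will be censored at last available study visit". SAP Section 3.3 treats systemic immunosuppressants other than prednisone as concomitant medications.

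**The concern.** The period over which the event can be observed and the period over which the subject counts as at risk do not match. Stopping ibrutinib/placebo for toxicity, noncompliance or investigator decision (Protocol 9.2) is not a competing event. Such a subject goes on attending response visits until cGVHD or malignancy progression, and the SAP keeps that subject in the risk set until the last visit. If another immunosuppressant is still being taken when medication recording closes, its later withdrawal is not a listed data item. The analysis would read the missing stop date as continued immunosuppression.

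The cumulative incidence functions compared by Gray's test are then too low. If non-competing discontinuation differs between arms, the comparison is distorted as well. Because testing is serial, a non-significant result at step 3 ends formal testing of steps 4 to 6. Step 2, steroid withdrawal, does not share the problem, because 8.3.1 does collect steroid requirements.

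**Working it through.** **1. The plan's own figure.** The only sample-size statement is for the primary endpoint (SAP 1.4: 30% v 50%, two-sided 5%, at least 80% power, 186 subjects). With mean rate 0.40:

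n per arm = [1.96 × √(2 × 0.40 × 0.60) + 0.8416 × √(0.30 × 0.70 + 0.50 × 0.50)]² / 0.20² = (1.358 + 0.571)² / 0.04 ≈ 93, so 186 in total, with 80.0% power.

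The figure reproduces. The point does not depend on it, and no event count or power is stated for the IST endpoint.

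**2. Who is affected.**

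| Subject's situation | Is a later IST withdrawal lost? |
|---|---|
| Still on ibrutinib/placebo | No; treatment visits review concomitant medications |
| Ibrutinib/placebo held for response (5.3.1.6) | No; a hold requires 12 weeks of maintained response after all immunosuppressants are off, so the event has already occurred |
| Started new cGVHD therapy | No; competing event |
| New therapy for malignancy progression | Normally no; relapse, a competing event, comes first |
| Off ibrutinib/placebo for a non-competing reason, still on prednisone | Depends on what 'or' means |
| Off ibrutinib/placebo for a non-competing reason, prednisone finished, other IST continuing | Yes, once 30 days have passed |

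**3. Confirmation.** An IST stopped d days after the last study treatment leaves 30 − d days of recorded observation. For any d above 0 this is shorter than the 30 days the event requires. So even a stop inside the window cannot be confirmed from data recorded within it.

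**4. Crude count.** Missed events = 193 × q × s × w, where q is the share on another IST at entry, s the share off study drug for a non-competing reason, and w the share of those who later withdraw the IST. All three are assumptions.

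- Low: 193 × 0.3 × 0.1 × 0.3 = 1.7
- Middle: 193 × 0.5 × 0.2 × 0.3 to 0.6 = 5.8 to 11.6
- High: 193 × 0.7 × 0.3 × 0.6 = 24.3

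This has no time limit and ignores competing events, so it overstates the loss.

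**5. Simulation with competing events.** There were 20,000 simulated subjects per scenario, with Aalen-Johansen estimates at 52 weeks. Assumed: 45% with a competing event by week 48; prednisone off at week 24 plus an exponential time of mean 26 weeks; other IST off 4 weeks plus an exponential time of mean 12 weeks after prednisone; last visit uniform between weeks 48 and 100. Here s is the share stopping study drug for a non-competing reason by week 48.

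| q | s | Full recording | Recording to 30 days after the later drug | To 30 days after ibrutinib/placebo | Shortfall, points |
|---|---|---|---|---|---|
| 0.3 | 0.1 | 0.367 | 0.362 | 0.361 | 0.5 to 0.6 |
| 0.3 | 0.3 | 0.366 | 0.352 | 0.352 | 1.4 |
| 0.5 | 0.1 | 0.320 | 0.311 | 0.311 | 0.9 |
| 0.5 | 0.2 | 0.329 | 0.312 | 0.311 | 1.7 to 1.8 |
| 0.5 | 0.3 | 0.326 | 0.299 | 0.297 | 2.7 to 2.9 |
| 0.7 | 0.1 | 0.289 | 0.276 | 0.275 | 1.3 to 1.4 |
| 0.7 | 0.3 | 0.287 | 0.254 | 0.252 | 3.3 to 3.5 |

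The simulation counts any stop inside the window as observed and does not apply the confirmation problem of step 3, so it is slightly lenient. It also follows the Table 4 order for everyone, which pushes the other way.

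**6. Between arms.** The shortfalls in step 5 are within one curve. If one arm had s = 0.3 and the other 0.1, with q = 0.7 in both, the gap would be 3.3 − 1.3 = 2.0 points. The standard error of a difference near 0.33 with 96.5 per arm is √(2 × 0.33 × 0.67 / 96.5) = 0.068, or 6.8 points, so that gap is about 0.3 of a standard error. With equal s there is no differential loss, but both curves are too low.

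**The case against.** The case for leaving this alone has real substance. A lost event needs several things together: another IST still in use, study drug stopped for a non-competing reason, prednisone also finished if 'or' means the later drug, IST withdrawal too late for the window, and no earlier competing event. The taper order is guidance with an exception, and Section 6.1.2 allows earlier tapering. The eCRF is not available, and the extent of the concomitant-medication row in Appendix A cannot be read, so fuller collection may exist in practice. SAP Section 1.5.3 intends to assess withdrawal of all systemic cGVHD therapies at the final analysis. The likely size is small beside sampling error.

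The limits on reach and size stand. The mismatch itself is not removed: two protocol sections state the end of recording, the follow-up list is consistent with them, and SAP Section 1.5.3 names no data source.

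A reader might infer that the gap biases the endpoint against ibrutinib. The documents do not support this, since they give no discontinuation rates by arm. Suppose 10 to 30% v 5 to 15% discontinue, with 25 to 50% of these withdrawing late. Pairing low with low and high with high gives 1.25 to 7.5 points against ibrutinib. The same ranges also allow 10% v 15%, which gives (0.10 − 0.15) × 0.25 to 0.50 = −1.25 to −2.5 points, the opposite sign. That product also ignores competing events and time.

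A reader might also infer that the primary censoring rule should be moved to the end of recording. That would tie censoring to treatment discontinuation, which may be informative for IST withdrawal and may differ by arm.

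**Conclusion.** The point holds in limited form. Followed as written, the plan leaves some withdrawals of existing immunosuppressants unobservable or unconfirmable and counts the time as event-free, on an endpoint ranked third in the gate. It concerns only subjects who leave study drug for a non-competing reason while another immunosuppressant continues.

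Under the assumed rates (30 to 70% on another IST at entry, 10 to 30% non-competing discontinuation by week 48, and the timings in the working), the 52-week cumulative incidence is understated by roughly 0.5 to 3.5 points. None of these rates comes from the documents. The arm with more non-competing discontinuations is understated more, and which arm that is remains unknown. It is worth correcting because the remedy is cheap and later formal tests depend on this step, not because a large bias has been shown.

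**What to change.** - **Protocol 8.3.1:** add start and stop dates of all systemic immunosuppressants at the visits already scheduled, until a competing event or the last visit, and for long enough to confirm 30 days off.
- **Protocol 6 and 7.1.1.4:** extend the recording window for these agents to match, and state whether 'or' means the later drug.
- **Missing dates:** retrieve them from source records. The SAP reports enrollment as complete at 193 subjects, so for visits already past this is the step that recovers data.
- **SAP Table 2:** keep the primary censoring rule. Where dates cannot be recovered, add a sensitivity analysis that censors this endpoint at the end of IST recording, with a note that such censoring may be informative.

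The cost is one data item per existing follow-up visit, some source-record retrieval and one added analysis. If the eCRF already collects these dates through follow-up, it is enough to say so in both documents and correct the stated window.

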#### **6.1. Permitted Concomitant Medications**

##### **6.1.1. Ancillary Therapy and Supportive Care**

Ancillary therapy and supportive care for cGVHD is permitted as outlined in the NIH Consensus Development Project 2014 Ancillary Therapy and Supportive Care Working Group Report (Carpenter 2015, Appendix L). In particular, the use of regimen to specifically treat or prevent bronchiolitis obliterans are allowed (eg, inhaled steroids/azithromycin/montelukast) and will not be considered systemic treatment for cGVHD.

Other supportive medications in accordance with standard clinical practice (such as for emesis, diarrhea, etc.) are permitted. Use of neutrophil growth factors (filgrastim and pegfilgrastim) or red blood cell growth factors (erythropoietin) is permitted per institutional policy. Transfusions may be given in accordance with institutional policy. Anti-fungal prophylaxis should be given as outlined in [Appendix L](#).

After consultation with the medical monitor the following may be considered; localized hormonal or bone sparing treatment for malignancies, and localized radiotherapy for medical conditions other than the underlying disease.

### **6.1.2. Systemic Immunosuppressant Therapy**

During the Screening period, the physician will have the discretion to start prednisone while eligibility for the study is being confirmed, however, the subject must be randomized within 7 days of initiating treatment with prednisone.

Addition of any other new systemic immunosuppressant therapy (including ECP) to treat cGVHD is prohibited during Screening and subsequent enrollment into the study. Addition of a new systemic immunosuppressant for cGVHD will be considered a treatment failure and ibrutinib/placebo will be discontinued.

At enrollment, subjects may be receiving other immunosuppressants for the prophylaxis or treatment of acute GVHD. Tapering of these other immunosuppressants upon start of ibrutinib/placebo or prednisone is permitted (see [Section 5.3.2.2.1](#)).

Use of immunosuppressants for reasons other than treatment for cGVHD should be discussed with the medical monitor.

## **6.2. Medications to be Used with Caution**

### **6.2.1. CYP3A Enzyme Inhibitors/Inducers**

Ibrutinib is metabolized primarily by CYP3A4. The dose of ibrutinib/placebo should be adjusted for concomitant use of CYP3A inhibitors per [Table 5](#) below:

**Table 5. Ibrutinib/Placebo Dose Modifications for Concomitant Use of CYP3A Inhibitors**

CYP inhibitor class	Dose modification instructions

 
Mild CYP3A inhibitors
 
	420 mg once daily. No dose adjustment required.

 
Moderate CYP3A inhibitors
 
	420 mg once daily. No dose adjustment required.

 
Voriconazole at any dose or
 
Posaconazole at doses less than or equal to suspension 200 mg BID or delayed-release tablet 300 mg QD
 
	280 mg once daily

 
Strong CYP3A inhibitors or
 
Posaconazole at higher doses
 
	140 mg once daily or consider alternative with less CYP3A inhibitory potential

Avoid concomitant use of strong CYP3A inducers ([Appendix D](#)). Consider alternative agents with less CYP3A induction and transition to a new agent within 4 weeks of randomization.

A list of common CYP3A inhibitors and inducers is provided in [Appendix D](#). For further information, please refer to the current version of the ibrutinib [IB](#) and examples of inhibitors, inducers, and substrates can be found at <http://medicine.iupui.edu/clinpharm/ddis/main-table/>. This website is continually revised and should be checked frequently for updates.

### 6.2.2. Drugs That May Have Their Plasma Concentrations Altered by Ibrutinib

In vitro studies indicated that ibrutinib is not a substrate of P-glycoprotein (P-gp), but is a mild inhibitor. Ibrutinib is not expected to have systemic drug-drug interactions with P-gp substrates. However, it cannot be excluded that ibrutinib could inhibit intestinal P-gp after a therapeutic dose. There is no clinical data available. Therefore, to avoid a potential interaction in the GI tract, narrow therapeutic range P-gp substrates such as digoxin, should be taken at least 6 hours before or after ibrutinib/placebo.

